9 INVESTIGATIONAL PLAN

9.1 Study Design

A maximum of 100 patients with resected, newly-diagnosed WHO Grade IV glioma will be enrolled in this study with the expectation that approximately 79 patients will be randomized to subsequent treatment after completion of radiation treatment with concurrent temozolomide. At the time that accrual to Groups I and II are complete an interim analysis will be conducted in order to make a decision concerning the accrual of additional patients to address efficacy objectives within patients subgroups defined by CMV status (see Section 15.8). The study was

closed to enrollment in April 2018 (Amendment 73). All patients previously enrolled will continue on study as planned.

All enrolled patients will undergo a leukapheresis after resection for harvest of PBLs for generation of DCs. Patients will then receive approximately 6 weeks of standard of care RT and concurrent TMZ at a standard targeted dose of 75 mg/m²/d (please see Package Insert uploaded in eIRB for standard therapy). Patients should start RT within approximately 6 weeks of surgery. Patients who either experience progressive disease during radiation, are dependent on steroid supplements above physiologic levels at time of first vaccination, are unable to tolerate TMZ, or whose DCs or PBLs fail to meet release criteria will be withdrawn from the study and replaced and will not undergo repeat leukapheresis. For patients whose initial leukapheresis yields less than 3 vaccines, repeat leukapheresis may be obtained a minimum of 2 weeks from the previous leukapheresis (and may be repeated as needed) if pre-pheresis blood work is within the Apheresis Center's parameters and as long as this does not cause a significant delay in treatment for the patient. At the post-RT clinic visit where patient's MRI and blood work is evaluated prior to ordering the first post-RT cycle of TMZ, patients will be randomized to receive DC vaccination with one of three treating regimens: Group I: unpulsed DC pre-conditioning prior to vaccination #4; Group II: Td pre-conditioning prior to vaccination #4; or Group III: basiliximab infusions at vaccination #1 and #2 with Td pre-conditioning prior to vaccination #4. As of March 2017 (AMD 49), randomization of patients to Group III has been terminated. Please see Section 9.1.1 for a detailed outline of the randomization strategy for vaccine site pre-conditioning and Section 9.1.7 for a detailed description of the double blinding process. The study cycle of TMZ comprises a targeted dose of 150-200mg/m²/d for 5 days every 5 (± 1) weeks. All patients will receive up to a total of 10 DC vaccines given bilaterally at the groin site unless progression occurs. DC vaccines will be given i.d. and divided equally to both inguinal regions. DC vaccines #1-3 will be given every two weeks, thus delaying the initiation of TMZ cycle 2 for all patients. All remaining TMZ cycles will continue every 5 (± 1) weeks. Before the first DC vaccination, patients will receive 0.5 mL of Td (tetanus and diphtheria toxoids adsorbed) intramuscularly into the deltoid muscle to ensure adequate immunity to the tetanus antigen. The Td vaccine will be obtained through Duke Investigational Chemotherapy Services (ICS) Pharmacy. All patients will undergo leukapheresis again for immunologic monitoring with specific assessment of baseline antigen-specific cellular and humoral immune responses and further DC generations 4 ± 2 weeks after vaccine #3.

If the patient is determined to have progressive disease, the patient may be considered for eligibility on the INTERCEPT study (INTracerebral EGFR-vIII Chimeric Antigen Receptor Gene-Modified T Cells for PaTients with Recurrent GBM, Pro00083828). If the patient is determined to be eligible for the INTERCEPT study (Pro00083828), the cells extracted from leukapheresis while they were on this study, ELEVATE, will be used to create the CAR T cells for administration in the INTERCEPT study.

Group I Treatment Plan (DC Vaccinations with pre-conditioning with Unpulsed DCs prior to the 4th DC vaccine) Patients in Group I will receive 1 x 10⁶ autologous unpulsed DCs in saline administered to a single side of the groin, and 0.4 mLs of saline administered to the contralateral side one day prior to the fourth DC vaccine, which is always given bilaterally at the groin site. Patients will then receive ¹¹¹In-labeled DCs as the 4th vaccine to compare the effects of different

skin preparations on DC migration followed by SPECT/CT imaging immediately and at 1 and 2 days after injections.

Group II Treatment Plan (DC Vaccinations with pre-conditioning with Td prior to the 4th DC vaccine)

Patients in Group II will receive a single dose of Td toxoid (1 flocculation unit, Lf, in 0.4 mLs) administered to a single side of the groin, and 0.4 mLs of saline administered to the contralateral side one day prior to the fourth DC vaccine, which is always given bilaterally at the groin site. Patients will then receive ¹¹¹In-labeled DCs as the 4th vaccine to compare the effects of different skin preparations on DC migration followed by SPECT/CT imaging immediately and at 1 and 2 days after injection.

Group III Treatment Plan (DC Vaccinations with basiliximab infusions prior to 1st and 2nd DC vaccine with Td pre-conditioning prior to 4th DC vaccine)

Patients in Group III will receive the first 3 DC vaccines every 2 weeks same as Groups I and II only they will also receive basiliximab 20 mg I.V. 7 days before DC vaccine # 1 and 7 days before DC vaccine # 2. Prior to the 4th vaccine, patients will receive a single dose of Td toxoid (1 flocculation unit, Lf, in 0.4 mLs) administered to a single side of the groin, and 0.4 mLs of saline administered to the contralateral side one day prior to the fourth DC vaccine, which is always given bilaterally at the groin site. This group will not undergo migration studies.

Effective March 2017 (AMD 49), randomization of patients to Group III has been terminated due to results from the related REGULATE study (IRB # Pro00000581), a study that evaluated the safety, toxicity, and efficacy of T Reg inhibition with basiliximab. REGULATE was used as the model for Group III in ELEVATE. Recent analyses of REGULATE data have shown that although the regulatory T cells were depleted, the cells did not show pp65 reactivity and their activation status was reduced. Patients previously randomized to Group III will continue on study as planned.

With AMD49, approximately 79 patients will ultimately be randomized to subsequent treatment after completion of radiation treatment with concurrent temozolomide, including 9 patients previously randomized to Group III. As originally planned, an interim analysis will be conducted after approximately 35 patients have been randomized to Groups I and II each in order to make a decision concerning the accrual of additional patients to address efficacy objectives within patient subgroups defined by CMV status (see Section 15.8).

All Groups

All patients will then be vaccinated in conjunction with subsequent TMZ cycles every 5 ± 1 weeks for a total of 6 to 12 cycles after RT at the discretion of the treating oncologist. DCs will be given on day 21 ± 2 days of each TMZ cycle. DC vaccinations will continue during TMZ cycles up to a total of 10 vaccines unless progression occurs. Patients will be imaged bimonthly at the discretion of the treating oncologist without receiving any other prescribed anti-tumor therapy. Patients will undergo an additional leukapheresis for generation of DCs if needed to continue vaccinations. As part of standard care for these patients, upon tumor progression, participants may undergo stereotactic biopsy or resection. As this is not a research procedure consent will be obtained separately. However, if tissue is obtained, it will be used to confirm

tumor progression histologically and to assess immunologic cell infiltration and pp65 antigen escape at the tumor site.

9.1.1 Randomization of Vaccine Site Pre-Conditioning Strategies

A randomization will be performed to assign patients to one of the three treatment strategies after completion of radiation with concurrent temozolomide. A permuted block randomization scheme stratified by *CMV* serology will be used to assign patients to treatment groups: unpulsed DCs pre-conditioning prior to vaccination #4, Td pre-conditioning prior to vaccination #4, or basiliximab infusions at vaccination #1 and #2 and Td pre-conditioning prior to vaccination #4.

As previously noted, the randomization of subjects to Group III has been terminated as of AMD 49. With this amendment, the randomization scheme stratified by *CMV* serology has been modified to assign patients to one of two treatment groups.

The administration of pre-conditioning agent (Td or unpulsed DCs) will be blinded for Groups I and II, however, the administration of the pre-conditioning agent (Td) and basiliximab for Group III will not be. Hence, patients and providers will know when a patient has been assigned to the third treatment group (please see randomization and blinding SOP 18.2 in appendices).

9.1.2 Definition of Unacceptable Toxicities

Toxicities will be graded according to the NCI CTCAE version 4 criteria. An unacceptable toxicity is defined as any Grade 3 toxicity that is possibly, probably, or definitely attributed to a study agent (basiliximab, pre-conditioning agent [Td or blinded Td/unpulsed DC], or pp65 DC vaccine) that does not resolve to baseline in 2-3 weeks, any Grade 3 hypersensitivity reactions or autoimmune toxicity requiring steroids or hormone replacement, any Grade 4 toxicity, including neurologic events not due to progressive disease, or any life-threatening event not attributable to concomitant medication, co-morbid event, or disease progression. A Grade 3 or greater toxicity that is clearly related to TMZ (an expected and known side effect) that does not resolve and requires an interruption, dose adjustment to metronomic TMZ schedule, or stoppage will result in subject removal from this protocol.

9.1.3 Dose Modification

TMZ will be administered concomitant with standard external beam RT under the direction of the oncologist. Please see TMZ package insert uploaded in eIRB for standard of care treatment guidelines. The dose may be adjusted at the discretion of the treating oncologist.

The study drug (*CMV* pp65 RNA-pulsed DCs) dose will not be modified in this trial. Those subjects whose cells fail to meet release criteria will be removed and replaced.

9.1.4 Safety Considerations

Management of Toxicities

If a Grade 3 NCI CTC or greater toxicity is seen that is not attributable to a concomitant medication, co-morbid event, or disease progression that has been documented radiographically or clinically, the next immunization for that patient will be withheld for up to 2 months or until the NCI CTC toxicity improves to a Grade 2 or until the KPS score returns to within 10 points of baseline. However, planned procedures requiring hospitalization, or long-term clinical decline that is now seen in patients years from WBRT, which are clearly not related to study drug, but

are the natural development common in this patient population, will not be considered an unacceptable toxicity nor will have immunizations withheld.

Adverse Event Reporting and Documentation

An “Adverse Event” will be defined as any adverse change from the subject’s pre-treatment baseline condition (which is assessed at the post-RT/TMZ clinic visit), including any clinical or laboratory test abnormality that occurs during the course of research after the time of randomization. Adverse events will be categorized and graded in accordance with the NCI CTC (Version 4).

A “Serious Adverse Event” will be defined as an undesirable sign, symptom or medical condition which: 1) is fatal or life threatening; 2) requires inpatient hospitalization or a prolongation of existing hospitalization; 3) results in persistent or significant disability/incapacity; 4) constitutes a congenital anomaly or a birth defect and/or; 5) medically significant such that it may jeopardize the subject, and may require medical or surgical intervention to prevent one of the outcomes listed above.

A summary of all adverse events (not just those considered related to study drug) that occur following randomization will be kept which will categorize the event by organ system, relationship to treatment, its grade of severity, and resolution. Periodic review by the PI and monthly review at the PRTBTC Adverse Event meeting of the collective adverse events will occur with the intention of identifying any trends or patterns in toxicity. If any such trends are identified, depending on their severity and frequency, a protocol amendment will be considered.

All adverse events which are serious and unexpected should be reported immediately to [name] ([contact]) or her designee [contact]) and to the FDA. Fatal or life-threatening, unexpected adverse events will be reported to the FDA by telephone, facsimile, or in writing as soon as possible, but no later than 7 calendar days after first knowledge by the sponsor followed by as complete a report as possible within 8 additional calendar days. Serious, unexpected adverse events that are not fatal or life-threatening will be reported to the FDA by telephone, facsimile, or in writing as soon as possible, but no later than 15 calendar days after first knowledge by the sponsor.

All adverse events that are considered serious, unanticipated, and related or possibly related to the research (as defined by 21CFR312.32[a]) will be reported to the Duke University Medical Center IRB using the appropriate SAE report form. At the time of the annual progress report to the Duke University Medical Center IRB, a summary of the overall toxicity experience will be provided.

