12.3 End of Treatment

Vaccines are given as described above for a total of 10 or until progression (whichever comes first). Once the vaccinations are complete, the treatment phase of the study will be over and the follow-up period will begin.

If the patient is determined to have progressive disease, the patient may be considered for eligibility on the INTERCEPT study (INTracerebral EGFR-vIII Chimeric Antigen Receptor Gene-Modified T Cells for PaTients with Recurrent GBM, Pro00083828). If the patient is determined to be eligible for the INTERCEPT study (Pro00083828), the cells extracted from leukapheresis while they were on this study, ELEVATE, will be used to create the CAR T cells for administration in the INTERCEPT study.

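### Unacceptable study-agent toxicity is defined without an action, and the only hold rule lets pp65 DC vaccination resume after it

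*Combined protocol and SAP*

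**What the plan says.** Section 9.1.2 of the protocol lists what counts as unacceptable:

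- a Grade 3 toxicity at least possibly attributed to the pp65 DC vaccine, the pre-conditioning agent or basiliximab "that does not resolve to baseline in 2-3 weeks, any Grade 3 hypersensitivity reactions or autoimmune toxicity requiring steroids or hormone replacement";
- every Grade 4 toxicity, neurologic ones included unless progression explains them;
- a life-threatening event with no other explanation.

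The list ends without a consequence. The sentence after it, on unresolved Grade 3 or greater toxicity clearly due to TMZ, does have one: interruption, "dose adjustment to metronomic TMZ schedule, or stoppage will result in subject removal from this protocol".

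Section 9.1.4 (Management of Toxicities) covers any Grade 3 or greater toxicity not explained by another drug, a co-morbid event or documented progression. The next immunization "will be withheld for up to 2 months or until the NCI CTC toxicity improves to a Grade 2". A third way for the hold to end follows: recovery of KPS to no more than 10 points from its baseline value. The same paragraph excludes planned hospital procedures and late decline after radiation; these "will not be considered an unacceptable toxicity nor will have immunizations withheld".

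On duration, 9.1 says "DC vaccinations will continue during TMZ cycles up to a total of 10 vaccines unless progression occurs", and 12.3 gives the same two end points. Section 9.1.3 rules out any change to the pp65 DC dose. Section 12.6.1 lists adverse events among the reasons for which the PI may withdraw a patient. Section 9.1.5 leaves the rescheduling of a missed vaccine to the PI.

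**The concern.** A protocol that labels certain events unacceptable would normally say what happens next. Here the background drug has a mandatory exit and the investigational agents do not. A clinician who follows the written hold can give the next dose, unreduced, to a patient whose last reaction the protocol itself calls unacceptable.

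What is at stake is the safety of patients still on vaccine. Enrollment closed in April 2018, but 9.1 says that patients already enrolled continue as planned. Of the three named agents, the vaccine is the one that matters in practice. Intradermal pre-conditioning is a single dose before vaccine #4. Basiliximab is given only before vaccines #1 and #2, and randomization to Group III ended in March 2017.

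**Working it through.** The plan gives no figure to reproduce and no toxicity rate, so the check is textual.

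**Step 1: look for a mandatory stop after study-agent toxicity.**

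- 9.1 and 12.3: vaccination ends at 10 doses or progression. Toxicity is not named.
- 9.1.2: removal, for TMZ toxicity only.
- 9.1.4: a hold, with no separate treatment of events that meet 9.1.2.
- 9.1.5: a missed dose may be rescheduled at PI discretion.
- 10.1: a binding resume rule requiring full recovery, but only after a positive sterility or mycoplasma test. The same section states that basiliximab is contraindicated in known hypersensitivity to it.
- 12.6.1: the PI may withdraw a patient. The list is permissive.
- 13.3: after an allergic reaction to pre-conditioning, the PI is alerted and approves unblinding. Nothing is said about later vaccines.

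None of these requires pp65 DC vaccination to end after an unacceptable study-agent toxicity.

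**Step 2: apply the 9.1.4 hold to events that meet 9.1.2.** The release conditions are joined by 'or'. The loose reading lets any one of them end the hold. The strict reading requires both Grade 2 and KPS recovery, with 2 months as a maximum. In cases A to C, KPS is taken to be within 10 points of baseline. Day 22 lies beyond both ends of the window in 9.1.2 (2 × 7 = 14 days; 3 × 7 = 21 days).

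| Case | Unacceptable under 9.1.2? | Hold ends, loose reading | Hold ends, strict reading |
|---|---|---|---|
| A. Related Grade 3, at Grade 2 on day 22, not at baseline | Yes | Yes | Yes |
| B. Grade 3 hypersensitivity that needed steroids, now Grade 2 | Yes | Yes | Yes |
| C. Grade 4, now Grade 2 | Yes | Yes | Yes |
| D. Related Grade 3, still Grade 3 at 2 months, KPS not recovered | Yes | Yes, on time alone | No; what follows is not stated |
| E. Related Grade 3, still Grade 3 after 3 weeks, KPS within 10 points | Yes | Yes, on KPS alone | No |

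Cases A to C do not depend on how 'or' is read. Case A is a direct mismatch: 9.1.2 asks for return to baseline, while 9.1.4 accepts Grade 2. Cases D and E arise only on the loose reading, which is the literal one.

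**Step 3: the window itself.** A related Grade 3 event that returns to baseline on day 18 is unacceptable if the limit is 14 days and acceptable if it is 21. The text does not say which applies.

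**The case against.** The strongest reply is that a hold combined with investigator judgment is a coherent policy for autologous cells in Grade IV glioma. Section 9.1.4 mentions unacceptable toxicity and withheld immunizations together, so the hold may well be the intended consequence of 9.1.2. The PI can withdraw a patient for adverse events and controls the rescheduling of missed doses. The PI is also alerted after an allergic reaction to pre-conditioning. Section 13.5 establishes a DSMBplus, and 13.4 says that safety committee reviews include stopping rules where applicable. The SOPs, monitoring plan and DSMBplus charter (18.2, 18.5, 18.6) are separate uploads and may state an action. Finally, a limit of up to 2 months reads more naturally as a cap on delay than as leave to dose through Grade 3 toxicity.

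Much of this stands. A reader might infer that the protocol directs re-dosing after an unacceptable event, or that nothing guards against it. The documents support neither: re-dosing is permitted rather than required, and several people can stop it. The finding is limited to the protocol text.

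What does not stand is that this settles the matter. If the hold is the intended consequence, it still ends at Grade 2 in cases A to C. If 2 months is a cap, the text does not say whether dosing or discontinuation follows. Discretion is not a rule, and 13.5 gives potential conflict of interest over the vaccine as the reason for the DSMBplus, which favors a written rule. Whatever the uploads contain, 9.1.2 and 9.1.4 should agree with each other.

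**Conclusion.** The concern holds as a minor patient-safety point. The protocol text defines unacceptable study-agent toxicity, states no action for it, and lets the hold end at 2 months, at Grade 2 or on KPS recovery alone. It therefore permits another unreduced pp65 DC dose after such an event and, read literally, while Grade 3 or worse toxicity persists.

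The size cannot be expressed as a number of patients or doses. The documents give no toxicity rate, and the schedule remaining for late enrollees would show only how many doses were planned, not how many would follow an unacceptable event. A reader might also infer a flaw in the survival or migration analyses, but no endpoint definition or analysis depends on this wording.

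The conclusion assumes that the uploads not seen here do not already impose a stop. If they do, the remaining fault is inconsistency between 9.1.2 and 9.1.4.

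**What to change.** Make one wording amendment with three parts.

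1. In 9.1.4, state that vaccination resumes only when the toxicity is Grade 2 or lower and KPS is within 10 points of baseline, and that it stops permanently if this is not met within 2 months.
2. In 9.1.2, attach an action by agent. An event that meets the definition and is at least possibly attributed to the pp65 DC vaccine ends vaccination. One attributed to basiliximab ends further basiliximab. One attributed only to the pre-conditioning dose needs a documented PI decision before the next vaccine. Survival follow-up continues under 12.6.2 in every case.
3. In 9.1.2, set the resolution window at 3 weeks.

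A blanket stop for any study agent would go too far. Pre-conditioning is not repeated, and of the two blinded arms only Group II receives Td intradermally. Ending all later vaccines after a Td reaction could make vaccine exposure differ between the arms compared for survival.

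The cost is small: no new visits, tests or patients. A few patients may stop vaccination earlier. They include one whose vaccine-related Grade 3 event is at Grade 1 but not baseline at 3 weeks, and one with vaccine-related Grade 3 autoimmune toxicity controlled by hormone replacement, because the protocol's own definition covers both. Survival data are kept, since 12.6.2 follows randomized patients until death or loss to follow-up. One limit remains: vaccines #1 to #3 are 2 weeks apart, so a dose can still be given at Grade 2 before a 3-week window closes.

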9.1.5 Missed Doses

To ensure that repetitive DC vaccines will be given to patients, DCs will be given on day 21 ± 2 days of each TMZ cycle. Therefore, with a margin of 2 days surrounding each TMZ cycle Day 21, all patients will receive up to 10 DC vaccines or until progression, whichever comes first. At the discretion of the study PI, patients who miss vaccine administration for whatever reason will have their appointment re-scheduled to administer the vaccine as soon as possible and a deviation will be filed with the Duke IRB. For continued non-compliance with the scheduled vaccine appointments, the subject may be removed from the trial at the discretion of the study PI.

